#### Phase I – Safety study

##### Primary outcome measure

- Safety: Determine serious adverse reactions or adverse reactions from the application of GM-CSF, metronidazole and fosfomycin in the pouch as seen in Appendix 8. The category of the reactions will be determined by the principal investigator according to the safety assessment described in chapter 7.  
A summary of the product characteristics of GM-CSF, fosfomycin and metronidazole will function as a reference document in evaluation of adverse effects. We will monitor adverse reactions from the day of the intervention in Phase I and II until respectively day 30 and 37. The safety of the intervention will be measured by adverse reactions.

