### Phase I

Tolerability of the treatment is tested on 6 patients with a single dose of the combined medication applied endoscopically. See also appendix 14 for a flow-chart.

Patients will be identified by the treating gastroenterologist through the outpatient clinic when presenting with pouchitis and then informed in detail and screened according to the inclusion and exclusion criteria. The patient then gets at least 24 hours to reflect before signing the informed consent form to enter the trial.

- Day 1:
  - Clinical examination is performed and pre-treatment blood samples taken
  - Endoscopy with biopsies is performed and GM-CSF, metronidazole and fosfomycin is sprayed into the pouch as a single dose
- Day 7:
  - Clinical examination, post-treatment blood samples,
  - Endoscopy with biopsies
  - Recording of any adverse reactions or other adverse events (can be any day between day 6-9)
- Afterwards, the patient receives the standard treatment at Zealand University Hospital for acute pouchitis, consisting of a 10-day course of oral metronidazole 500 mg x 3 or ciprofloxacin 500 mg x 2.
- Day 30:
  - Telephone call to the patient to ask about symptoms of pouchitis and any side effects. (Can be any day between day 30 and 37).

After the last patient in phase I has had their 30 day follow-up, the safety and feasibility of the study drug application will be assessed by the sponsor and investigators of the study. If no serious adverse events of reactions occurred, the Phase II study will be initiated.

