#### Reasons for withdrawal

A patient will be discontinued from participation in the study

- if any clinical AE or AR (adverse event or reaction), laboratory abnormality, intercurrent illness, or other medical condition or situation occurs which suggests that continued participation in the study would not be in the best interest of the patient. This also concerns the necessity of initiating a particular drug treatment, e.g. antibiotics for infection or taking a 'rescue drug' for a medical condition, that interacts with the study drug
- when developing any of the exclusion criteria

Patients can voluntarily withdraw from participation in this study at any time as well as withdraw from receiving the study intervention for any reason. The patients will be informed of this right in accordance with the Helsinki Declaration.

The investigator can withdraw a patient if the investigator considers that the safety of the patient is compromised by the participation in the study. In that case, the investigator must inform the patient about the reason for withdrawal.

When patients withdraw from the study, reasons for withdrawal, if given, will be documented in the CRFs (Case report forms). The number of dropouts and withdrawals will be reported. No further data will be collected from the patients withdrawing from the study; however, the previously collected data will be part of the final data analysis unless the patient specifically requests all data to be deleted. Patients that have received the study medicine will be contacted by telephone two weeks after receiving the study medicine, to ensure patient wellbeing. This data after withdrawal from the study, will not be collected and is meant solely to ensure the safety of the patient.

In case of withdrawal due to AE or AR, safety data will be collected and the patient will be followed until given appropriate care under medical supervision or until symptoms of any AE or AR resolve or become stable.

Participants who discontinue early will be replaced. This concerns all patients that have not undergone the second endoscopy. In case of withdrawal due to a serious adverse event (SAE) or serious adverse reaction (SAR), continuity of inclusion will be discussed with the sponsor.

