### **Enrollment meeting**

Patients who are eligible for inclusion will receive both oral and written information about the study. The oral information will be delivered in a room only used for that purpose to avoid disturbances. The patient can be offered to have the enrollment meeting at his/her home. The investigator will have enough time to explain the content, extent, purpose, expected risks and advantages of the study in plain Danish or English. The patient will have enough time to read the written information and to ask questions. The following will be covered during the interview:

- The purpose and organization of the study
- The procedures during the therapeutic endoscopy
- The permission to access the patient's files to register any adverse reaction, medication use, blood tests and other clinical parameters perioperatively, and that this permission will also give the sponsor, the investigators, the Danish Medicines Agency, the GCP unit (Good clinical practice unit), and the Danish Data Protection Agency access to patient files during monitoring
- The methods used in the study
- The right to ask for additional information at all times
- The right of the patient to withdraw at any time during trial without explanation
- The insurance
- The contact person

At the end of the enrolment meeting the patient may sign the informed consent if they wish, and may also be given the time needed for consideration (at least 24 hours). The informed consent will be written in accordance with Danish law (see Annex III). Patients will be informed if any changes in the study occur, as this might influence the patient's willingness to participate or the safety of the participating patients. The approved document will be updated accordingly.

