### **Serious adverse events or reactions**

An AE or AR is considered serious when resulting in death, is life-threatening, results in hospitalization or prolongation of existing hospitalization, causes persistent or significant incapacity or substantial disruption of the patient's daily activity or causes a congenital anomaly or birth defect, and other adverse events that according to the investigator's judgement are medically significant. A medical event that

requires surgery or medical intervention to prevent one of these outcomes is also considered a serious AE or AR. All SAE (Serious adverse events) and SAR (Serious adverse reactions) will be recorded on the appropriate form, and followed through resolution by the investigator as well as reviewed and evaluated.

All SAE and SAR will be registered and reported to the sponsor by the investigator within 24 hours after the event has been recorded by e-mail. All adverse reactions will be reported to the Danish Medicines Agency and the local Ethics Committee in an annual report with a report on patient safety of the trial. All SAR will be reported in an annual report together with a report on patient safety to the Danish Medicines Agency. All SAE and SAR will be evaluated by the investigator according to the known possible adverse reactions reported in the product summary (see below) if they are a possible SUSAR (Suspected unexpected serious adverse reaction).

As there are no previous data on the administration of GM-CSF, fosfomycin and metronidazole in the pouch, there are no data on expected serious adverse events or reactions in the reference safety information of the Investigator's Brochure of GM-CSF. Therefore, all SAE and possible SAR are considered to be related to the investigational medicinal product and will be reported as SUSAR.

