## 8. Statistical considerations

We plan to include 6 patients in the Phase I study to test tolerability, and 12 patients in the Phase II study to test effectiveness of the treatment. The trial will end with the last visit of the last patient (Day 37 of the last patient). This is a safety and clinical proof-of concept intervention study, and we are, to the best of our knowledge, the first group to look into local treatment with GM-CSF and antibiotics of biofilm in patients with pouchitis after IPAA for ulcerative colitis. We expect this number of patients to be sufficient to provide the necessary experience in implementing the technique and form a basis for future studies, including future sample size calculation. This is based on calculations on number of patients required to achieve statistical significance of paired before-and-after comparisons by non-parametric tests. To achieve statistical significance at 1% level in Phase II, 9 patients are needed. As there is a risk of patients withdrawing from the trial prematurely or not receiving all interventions, we aim to include 3 additional patients.

Our primary objective is to test for adverse events or reactions in Phase I and a significant change in PDAI in Phase II, defined by a decrease of 3 points. Differences pre- and post-treatment will be described by means and standard deviations, or median and range when appropriate, and will be analyzed by the appropriate statistical tests. All patients described in chapter 5 as 'Completed test persons' will be included in the statistical analysis.

Microbial diversity changes will be analyzed using PERMANOVA (permutational analysis of variance). Other secondary objectives like change in WBC and CRP will be analyzed using the appropriate statistical tests.

Data will be analyzed using non-parametric or parametric statistics depending on the distribution of the data. P-values  $\leq 0.05$  are considered significant. Correction for multiple comparisons will be performed if needed. Descriptive statistics will be used for baseline characteristics.

Missing data will be handled depending on the type of data missing. If missing data results in a patient not being able to be defined as a 'Completed test person' (Chapter 5), the patient is excluded from the trial and a new patient will be recruited. If individual results are missing (e.g. laboratory values), the last known values will be used for analysis.

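### What a dosed patient who has withdrawn reports at the two-week safety call is by rule not collected, so a non-serious reaction can be lost from the Phase I primary outcome, and the rule conflicts with the duty to register serious events

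*Protocol*

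**What the plan says.** Section 5, Reasons for withdrawal, gives these rules for a patient who leaves the study:

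- Data collection stops: "No further data will be collected from the patients withdrawing from the study". Data gathered before withdrawal stay in the final analysis unless the patient asks for deletion.
- A safety call still takes place: "Patients that have received the study medicine will be contacted by telephone two weeks after receiving the study medicine, to ensure patient wellbeing".
- The content of that call is set aside: "This data after withdrawal from the study, will not be collected and is meant solely to ensure the safety of the patient".
- There is one exception. If the withdrawal was due to an adverse event or reaction, safety data are collected and the patient is followed.
- Anyone without the second endoscopy is replaced.

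Elsewhere the protocol sets monitoring duties with no carve-out for withdrawn patients:

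- Section 3, the Phase I primary outcome: "We will monitor adverse reactions from the day of the intervention in Phase I and II until respectively day 30 and 37". Section 7 (Unexpected adverse event) repeats this window.
- Section 7, Safety assessments, requires adverse events during and after administration to be reported, and non-serious ones to be entered on a form.
- Section 7, Serious adverse events or reactions: "All SAE and SAR will be registered and reported to the sponsor by the investigator within 24 hours".

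Section 4, Phase I, bases the move to Phase II on a safety and feasibility assessment by the sponsor and investigators, with one explicit condition: "If no serious adverse events of reactions occurred, the Phase II study will be initiated".

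**The concern.** This is not a gap that a statistical analysis plan could fill. It tells site staff not to collect safety information they have actively obtained.

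The exception covers only part of the risk. Patients are told of "The right of the patient to withdraw at any time during trial without explanation", and section 5 documents reasons only where they are given. Two kinds of patient are exposed: one who leaves for an unrelated reason and reacts afterwards, and one who leaves feeling unwell, gives no reason, and is not recognised as a withdrawal due to an adverse event.

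Adverse reactions are the Phase I primary outcome, and they inform the step from a single dose to daily dosing for a week. If patients who feel unwell are more likely to leave, which is plausible but not documented, the loss biases the reaction count downward. With so few patients, one missing reaction changes the summary from some to none.

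**Working it through.** The protocol gives no figure to reproduce here: the Phase I size has no stated calculation. The check sets the rules side by side and then illustrates the possible effect.

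**Step 1. Is the call inside the outcome window?** Phase I dosing is on Day 1, so two weeks later is Day 1 + 14 = Day 15, before Day 30. In Phase II, counting from the first dose (Day 1) gives Day 15 and from the last (Day 7) gives Day 21, both before Day 37. The call is inside the window in either phase.

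**Step 2. What happens to a reaction first heard of at the call?**

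| Situation | Section 5 | Other sections | Result |
|---|---|---|---|
| Withdrawal due to AE/AR | Collected, followed | Same | Recorded |
| Other or unstated reason, non-serious reaction | Not collected | Section 7 requires AE capture | Conflict; lost if section 5 is followed |
| Other or unstated reason, serious reaction | Not collected | Section 7 requires registration and reporting to the sponsor | Direct conflict |

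**Step 3. Does the patient stay in the denominator?** Section 8 builds the statistical analysis on completed test persons and excludes and replaces those who do not qualify. A Phase I patient who leaves before the second endoscopy (Day 6–9) is therefore replaced. Section 5 says data from before withdrawal are kept, but nothing in section 8 keeps that patient in the safety count.

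**Step 4. Illustration.** From section 8: "We plan to include 6 patients in the Phase I study to test tolerability". Assumptions, none of them in the documents: one dosed patient withdraws before the second endoscopy for a reason not recognised as an AE/AR, is replaced, and first reports at the call a reaction outside the lists of known effects in section 3; the six completers have none. Exact (Clopper-Pearson) 95% limits:

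- Reported, 0/6: upper limit = 1 − 0.025^(1/6) = 45.9%. Result 0% (0 to 45.9%).
- With the call recorded, 1/7 = 14.3%: lower limit = 1 − 0.975^(1/7) = 0.4%; the upper limit solves (1−p)^7 + 7p(1−p)^6 = 0.025, giving 57.9%.
- Two such patients: 0/6 reported against 2/8 = 25% (3.2 to 65.1%).
- If the patient instead withdraws after the second endoscopy but before the call, there is no replacement: 0/6 reported against 1/6 = 16.7% (0.4 to 64.1%).

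**Step 5. The effect without assuming that the patient reacts.** Chance of at least one reaction = 1 − (1−p)^n, with seven dosed but six counted, for assumed true rates p:

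| p | n = 7 | n = 6 |
|---|---|---|
| 5% | 30.2% | 26.5% |
| 10% | 52.2% | 46.9% |
| 20% | 79.0% | 73.8% |
| 30% | 91.8% | 88.2% |

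The loss is about 4 to 5 percentage points per uncounted patient if withdrawal is unrelated to the reaction, and more if it is related.

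**The case against.** The strongest reply is that the protocol has safeguards and that section 5 is a deliberate, specific rule for people who have left the study. Much of this stands:

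- **Serious events.** A reader might infer that a serious event can slip past the Phase II start condition. The documents do not support that as stated. Section 7 requires every serious event and reaction to be registered and reported to the sponsor and treats them all as suspected unexpected reactions; section 8 involves the sponsor promptly and allows a halt. The condition fails only if section 5 is read as overriding those duties, and it does not say that it does. What remains is a conflict to settle.
- **Unexplained withdrawals.** A reader might infer that anyone who leaves without a reason is outside the exception. The exception turns on the cause, not on when it is disclosed, so it could apply if the cause emerges on the call. The text leaves this open.
- **Last contact.** Section 5 does not call the two-week call the last contact, and section 7 lets patients telephone throughout the trial.
- **The first two weeks.** It would be wrong to say that everything up to Day 15 goes unrecorded: data from before withdrawal are kept.
- **Reactions that count.** Section 3 already excludes many known effects from registration as adverse reactions for every patient, so the call changes that count only for reactions outside those lists.
- **Consent.** A patient may refuse further data use. But the rule discards the information even when the patient takes the call, answers freely and does not object.

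The argument that a specific rule displaces general ones does not rescue the text. It would settle which rule a site follows, and the result would be loss of primary-outcome data.

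**Conclusion.** The point holds in limited form. A reaction first disclosed at the two-week call by a dosed patient whose withdrawal was not due to an adverse event or reaction is left unrecorded by rule, within the window that defines the Phase I primary outcome. Non-serious reactions can be lost from that outcome and from the assessment before Phase II. For serious events, sections 5 and 7 contradict each other and must be reconciled; the documents do not show that such an event would in fact escape the start condition.

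The size, 0/6 reported in place of 1/7, is an illustration resting on one assumed patient and the conditions listed with it. The protocol gives no withdrawal rate, and the two intervals overlap widely. What is certain is the rule and the direction in which it can bias the count.

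**What to change.** Replace the sentence in section 5, Reasons for withdrawal, with three provisions:

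1. For every patient who received study drug, whatever the reason for withdrawal, adverse events learned at the two-week call are entered on the AE form unless the patient objects to further data use.
2. The duties in section 7 on serious events and reactions apply to withdrawn patients.
3. All dosed patients, replaced or not, stay in the Phase I safety denominator and in the safety review before Phase II. Section 8 should say that the completer set does not govern the safety outcome.

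The cost is small: amended protocol and consent wording, and documentation of a call already planned, with no added visit or procedure. Patients who refuse further data use still cannot be followed; their number should be reported beside the safety count.

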#### **Safety assessments and adverse events or reactions**

An adverse event (AE) is any untoward medical occurrence in a patient or clinical investigation subject that has been given a pharmaceutical product, regardless of its causal relationship to the study treatment. This can be an abnormal laboratory finding, a symptom or disease coincident in time with the use of the investigational medicinal product.

During and after administration of GM-CSF, fosfomycin and metronidazole, any adverse events or intercurrent illnesses will be reported. Patients who have known allergy to GM-CSF, fosfomycin and or metronidazole are excluded from study participation. The administration of the study drug combination will be in the presence of a medical doctor, the principal investigator. Patients will be observed in the endoscopy unit for at least 1 hour after the first administration of the drug. In case of the occurrence of

an adverse event or serious adverse event, monitoring and further treatment steps will be taken according to the type and severity of reaction.

The severity of the AE will be assessed using the following grading system:

- Mild: requires minimal or no treatment, does not interfere with the patient's daily activities
- Moderate: low level of inconvenience or concern with therapeutic measures, some interference with the patient's daily activities
- Severe: interrupts a patient's daily activities, may require systemic drug therapy or other treatment, and is usually incapacitating
- Life threatening: places the patient at immediate risk of death from the reaction as it occurs

Changes in the severity of the AE will be documented.

All AEs, including both local and systemic events not meeting the criteria for 'serious adverse events' will be captured on the appropriate form for recording AEs. We will collect information on

- Description of the event
- Time of onset
- Clinician's assessment of the severity
- Relationship to the study product
- Time of resolution/stabilization of the event

Any medical condition that the patient has at baseline (time of inclusion in the study), will not be considered or reported as an AE. If an existing medical condition worsens during the study, it will be recorded as an AE.

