#### **Unexpected adverse event**

If an adverse event is not listed in the investigator brochure, it is considered 'unexpected'.

We will immediately report to the sponsor any unexpected serious adverse events, drug-related or not, including an assessment of whether we suspect the drug as the causative agent.

Adverse events and reactions will be monitored and followed up until end of the study and/or resolution of the adverse event or reaction, or until the adverse event or reaction is considered chronic.

The summary of the product characteristics and or investigator's brochure of GM-CSF, fosfomycin and metronidazole will function as a reference document for the evaluation of adverse effects. We will monitor adverse events and reactions from the day of the intervention in Phase I and II until respectively day 30 and 37. Monitoring will depend on asking patients if they have developed known adverse events or reactions as seen in Appendix 8, and self-reporting by the patient. Patients will have the possibility to contact the investigator by telephone during the duration of the trial, to report any adverse event or reaction. Patients will be encouraged to contact the relevant authority and initiate relevant help in case of serious acute adverse events or reactions.

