## Appendix 2 – Study schedules

### Phase I Study Schedule

		Follow-Up Schedule			
Procedures		Screening Day 0	Baseline Day 1	Follow-up Day 7	Follow-up Day 30
Signed Consent Form		X	X		
Assessment of Eligibility Criteria		X	X		
Review of Medical History		X	X		
Review of Concomitant Medications		X	X	X	X
Application of study drug			X		
Physical Examination	Complete	X		X	
	Symptom-Directed		X		
	Vital Signs		X	X	
Assessment of Adverse reactions			X	X	X
Clinical Laboratory	Chemistry	X		X	
	Hematology	X		X	
Histology	Endoscopy with Biopsies		X	X	
Microbiology			X	X	

Phase II Study Schedule

				Follow-Up Schedule		
Procedures		Screening Day 0	Baseline Day 1	Hospital administration Day 2-7	Follow-up Day 14	Follow-Up Day 37 (1 month after treatment)
Signed Consent Form		X	X			
Assessment of Eligibility Criteria		X	X			
Review of Medical History		X	X			
Review of Concomitant Medications		X	X		X	X
Application of study drug as enema			X	X		
Physical Examination	Complete	X			X	
	Symptom-Directed		X			
	Vital Signs		X		X	
Assessment of Adverse reactions			X	X	X	X
Clinical Laboratory	Chemistry	X			X	
	Hematology	X			X	
Histology	Endoscopy with Biopsies		X		X	
Microbiology			X		X	

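### Dosed patients who withdraw for a reason not identified as an adverse event or reaction drop out of non-serious safety recording, although the protocol monitors to Day 30 or 37 and still telephones them at two weeks

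*Protocol*

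**What the plan says.** Section 5 (Reasons for withdrawal) sets these rules:

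- General stop: "No further data will be collected from the patients withdrawing from the study".
- Earlier data are kept: "the previously collected data will be part of the final data analysis unless the patient specifically requests all data to be deleted".
- Dosed patients are telephoned two weeks after the study medicine, and of that contact the section says: "This data after withdrawal from the study, will not be collected and is meant solely to ensure the safety of the patient".
- One exception: "In case of withdrawal due to AE or AR, safety data will be collected", with follow-up of the patient.
- The reason for leaving is documented only where the patient gives one.
- Anyone who has not had the second endoscopy is replaced.

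Section 3 (Phase I, primary outcome measure) measures safety by adverse reactions: "We will monitor adverse reactions from the day of the intervention in Phase I and II until respectively day 30 and 37". Section 7 (Unexpected adverse event) repeats this for events and reactions together: "We will monitor adverse events and reactions from the day of the intervention in Phase I and II until respectively day 30 and 37". Section 7 (Safety assessments) adds that adverse events during and after administration are reported, and that non-serious ones "will be captured on the appropriate form for recording AEs". None of these places exempts withdrawn patients.

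Section 8 excludes a non-completer from the trial and recruits a replacement. Section 9 anonymises the data of a patient who withdraws.

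**The concern.** The investigator makes the two-week call anyway. If a withdrawn patient mentions a new non-serious reaction on it, sections 3 and 7 call for it to be counted and section 5 says it is not to be collected. Adverse reactions are the Phase I primary outcome, and only six patients are planned, so a single unrecorded reaction is visible in the result. Section 7 (Serious adverse events or reactions) states that there are no previous data on giving this combination in the pouch, so each dosed patient's safety information carries weight. This is a stated rule that discards information the trial will already hold, not a detail left for later.

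**Working it through.** No figure in the protocol rests on this rule, so there is nothing to reproduce. The check sets the texts side by side and then gives an illustration of size.

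**Step 1: who is caught.** The stop is worded for patients who withdraw from the study. Section 5 also recognises withdrawal from the intervention alone, and that patient need not be caught. Section 7 defines an adverse event broadly, whatever the cause, and includes abnormal laboratory findings, symptoms and diseases. Most investigator-driven grounds in section 5 (laboratory abnormality, intercurrent illness, infection needing antibiotics) are therefore adverse events, and those patients fall under the exception. What remains is mainly voluntary or unexplained departure, plus a few exclusion-criterion cases such as pregnancy.

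**Step 2: what is lost for those patients.**

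- Serious events: not lost. Section 7 has all of them registered and reported.
- Data recorded before withdrawal: kept under section 5, unless the patient asks for deletion.
- Non-serious events or reactions that arise, or are first reported, after withdrawal: lost. Section 3 does not register the listed known effects as adverse reactions for anyone, so the loss to the adverse-reaction count is of unlisted effects. The Appendix 8 tick-box record of listed effects goes too.

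**Step 3: what has been recorded by then.** In the Phase I schedule (Appendix 2) the row "Assessment of Adverse reactions" is marked at Days 1, 7 and 30. A patient who leaves before Day 7 has had 1 of 3 scheduled assessments, on the dosing day, plus any self-report. The missed Day 7 visit follows from the patient leaving. What the rule itself removes is the record of the two-week call (Day 1 + 14 = Day 15) and any Day 30 contact.

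**Step 4: illustration, all counts assumed.** Seven patients are dosed in Phase I. Six complete without a reaction. One leaves before the second endoscopy without giving a reason, is replaced, and reports one unlisted non-serious reaction on the call. Exact (Clopper-Pearson) two-sided 95% limits; for 0/n the upper limit is 1 − 0.025^(1/n).

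| Handling | Reported | 95% CI |
|---|---|---|
| Call recorded, all dosed patients counted | 1/7 = 14.3% | 0.4% to 57.9% |
| Call not recorded, replaced patient counted (section 5) | 0/7 = 0% | 0 to 41.0% |
| Call not recorded, replaced patient excluded (one reading of section 8) | 0/6 = 0% | 0 to 45.9% |

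**Step 5: direction.** Leaving out a reaction can only lower the count. Removing a replaced patient from the denominator is a separate matter and can work the other way. If one of six completers reacts and the replaced patient does not, excluding the latter gives 1/6 = 16.7% instead of 1/7 = 14.3%.

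**The case against.** The strongest reply is that section 5 is the specific rule for people who have left and sections 3 and 7 are the general one, so there is no contradiction. Ending data collection when someone exercises the right to withdraw is also a defensible default. Part of this stands: a patient who declines further data collection should not be followed for data. But the stop is not confined to such patients, and it covers those willing to take the call. Nor does the reading remove the loss, because the exception turns on the reason for leaving, which may never be stated, and a reaction can begin after departure.

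A second reply is that the safety population belongs in a statistical analysis plan, which is not shown. That is fair for its definition. Still, the protocol itself fixes two rules that do not sit together: section 5 keeps a withdrawn patient's earlier data in the final analysis, and section 8 excludes a non-completer from the trial.

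A reader might infer more than the documents support:

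- That serious events could be missed and the move to Phase II compromised. The explicit condition in section 4 is the absence of serious events, and these remain reportable.
- That every bias favours the drug. This holds for unrecorded reactions, but not for the reported proportion once replaced patients may leave the denominator (Step 5).
- That most of the monitoring window is lost. Such a percentage only subtracts an assumed withdrawal day from 30 or 37, and monitoring is by a few contacts plus self-report, not daily capture.

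**Conclusion.** The point holds in a narrow form. For dosed patients who withdraw from the study for a reason not identified as an adverse event or reaction, section 5 stops safety recording and sets aside a call already made, at odds with the monitoring in sections 3 and 7. The loss is of non-serious events or reactions arising or first reported after withdrawal. It affects the Phase I primary outcome and a Phase II secondary outcome.

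The size cannot be estimated, since the protocol gives no withdrawal rate. The comparison of 0/6 or 0/7 with 1/7 assumes one such patient and one such reaction, and shows only how much a single case weighs at this sample size. The point is worth fixing because the information is at hand and recording it is cheap, not because a large distortion has been shown.

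**What to change.** - **Section 5, Reasons for withdrawal:** replace the sentence that bars collection. Record the two-week call on the Appendix 8 form, and follow every patient who received any study drug for adverse events and reactions to Day 30 (Phase I) or Day 37 (Phase II), unless the patient declines further data collection.
- **Section 9 and the Danish Appendix 9 (researcher's access to data):** delay anonymisation of a withdrawn patient's data until this safety follow-up ends. Otherwise the later record cannot be linked to the patient.
- **Section 8:** limit the completed-test-person rule to the before-after comparisons, and state that safety is reported in all dosed patients, including those replaced.

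The cost is a formal protocol amendment with Ethics Committee approval, as section 10 (General considerations) requires for changed procedures, and one extra Day 30 or Day 37 call per withdrawn patient. The two-week call and the form already exist. Sample size, significance level and the efficacy analysis do not change.
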